8.2 Comparability of Subjects at Baseline

The statistical significance of any treatment group difference in the distribution of categorical variables such as gender will be tested using Cochran–Mantel–Haenszel (CMH) test for general association adjusted for site. Continuous variables, such as age, will be analyzed using a two-way analysis of variance (ANOVA) model with site and treatment as a fixed effect.

9. CONSENT/ASSENT CONSIDERATIONS AND PROCEDURES

It will be made clear to the subject that, for the purposes of the study, they are consenting only for topical application of medication or vehicle. Investigators may discuss the availability of the study and the possibility for entry with a potential subject without first obtaining consent/assent. However, informed consent/assent must be obtained and documented prior to initiation of any procedures that are performed solely for the purpose of determining eligibility for research, including withdrawal from current medication(s). When this is done in anticipation of, or in preparation for, the research, it is considered to be part of the research.

The study must be approved in writing by an appropriate IRB as defined by FDA regulations. A copy of the Letter of Approval from the IRB, which also contains specific identification of the documents approved, must be received by Perrigo prior to study commencement.

Periodic status reports must be submitted to the IRB at least annually as required by the site's IRB, as well as notification of completion of the study and a final report within three months of study completion or termination. A copy of all reports submitted to the IRB must be sent to Perrigo.

The investigator(s) has both ethical and legal responsibility to ensure that each subject being considered for inclusion in this study is given a full explanation of the protocol. This shall be documented on a written informed consent/assent form, which shall be approved by the same Institutional Review Board (IRB) responsible for approval of this protocol. Each informed consent/assent form shall include the elements required by FDA regulations in 21 CFR Part 50. The investigator agrees to obtain approval from Perrigo of any written informed consent/assent form used in the study, preferably prior to submission to the IRB.

Once the appropriate essential information has been provided to the subject and fully explained by the investigators (or a qualified designee) and it is felt that the subject understands the implications of participating, the IRB-approved written informed consent/assent form shall be signed by the subject (or their parent/legally authorized representative) and the person obtaining consent/assent (investigator or designee). The subject shall be given a copy of the signed informed consent/assent form and the investigator shall keep the original on file.

If the subject fails to meet the inclusion/exclusion criteria at the conclusion of the screening phase, the subject will be withdrawn from screening. In the event that the subject is re-screened for study participation, a new informed consent/assent form must be signed.

9.1 Subject Confidentiality

All participants are concerned for the individual subject's privacy and, therefore, all subject data will be identified only by a subject identification number and subject initials. However, in compliance with federal guidelines regarding the monitoring of clinical studies and in fulfillment of his/her obligations to Perrigo, it is required that the investigator permit the study monitor, a Perrigo authorized representative, and/or FDA representative to review that portion of the subject's medical record that is directly related to the study. This shall include all study relevant documentation including subject medical histories to verify eligibility, laboratory test result reports to verify transcription accuracy, admission/discharge summaries for hospital stays occurring while the subject is enrolled in the study and autopsy reports for deaths occurring during the study.

As part of the required content of informed consent/assent, the subject must be informed that his/her medical chart may be reviewed by Perrigo, Perrigo authorized representative, or a representative of the FDA. Should access to the medical record require a separate waiver or authorization, it is the investigator's responsibility to obtain such permission from the subject in writing before the subject is entered into the study.

To preserve the subject's confidentiality, the data collected will be available only to the investigators of the study, their support staff, Perrigo, and possibly the FDA.

All reports and communications relating to the subject in the study will identify each subject only by the subject's initials and by the subject number. The investigator agrees to furnish Perrigo with complete subject identification, if necessary on a confidential follow-up form, which will be used for the purpose of a long-term follow-up, if needed. This will be treated with strict adherence to professional standards of confidentiality and will be filed at Perrigo under adequate security and restricted accessibility.

10. RECORDS MANAGEMENT

10.1 Data Collection

Protocol No: PRG-NY-15-002

Database set-up will be performed by [REDACTED] in collaboration with the Electronic Data Capture (EDC) vendor, using an appropriate fully validated, 21 CFR Part 11 compliant Electronic Data Capture (EDC) system. eCRFs will be provided to each site via a secured web link. All applicable study data collected on each subject will be recorded by approved site personnel into the eCRF. Only authorized site personnel will be able to enter/modify/correct data to the eCRF.

Approved staff at [REDACTED] will verify all data entered into eCRFs for completeness and accuracy with reference to the source documents and records and will issue manual data queries to correct missing data or discrepancies found against the source within the EDC system.

Data validation will consist of automated and manual edit checks that are created directly into EDC. Automated edit checks will be executed on all data points defined and documented by the study team and data management. Study metrics will be reported from the EDC system.

After all data have been verified by approved staff at [REDACTED], an Investigator or Sub-Investigator (listed on Form FDA 1572) is required to review and approve all eCRFs prior to database lock and breaking of the blind.

After database lock, each site will be provided with a CD that will include the eCRF data from their site for local archival purposes.

Quality assurance verification via a 10% database audit of eCRF data will be conducted before the treatment assignment code is broken.

10.2 Source Documents

Source documents are defined as the results of original observations and activities of a clinical investigation. Source documents will include, but are not limited to, progress notes and screening logs. All source documents pertaining to this study will be maintained by the investigators and made available for inspection by authorized persons. The original signed informed consent form for each participating subject shall be filed with records kept by the investigators and a copy given to the subject.

10.3 File Management at the Study Site

It is the responsibility of the investigator to ensure that the study center file is maintained in accordance with Section 8 of the International Conference on Harmonization (ICH) Guideline for Good Clinical Practices (GCP).

10.4 Records Retention at the Study Site

FDA regulations require all investigators participating in clinical drug studies to maintain detailed clinical data for one of the following periods:

- a) A period of at least two years following the date on which a New Drug Application is approved by the FDA;
- b) A period of two years after Perrigo New York notifies the investigator that no further application is to be filed with the FDA.

Protocol No: PRG-NY-15-002

The investigator must not dispose of any records relevant to this study without either (1) written permission from Perrigo New York or (2) providing an opportunity for Perrigo to collect such records. The investigator shall take responsibility for maintaining adequate and accurate electronic or hard copy source documents of all observations and data generated during this study, including any data clarification forms (DCF) received from Perrigo. Such documentation is subject to inspection by Perrigo and the FDA.

11. QUALITY CONTROL AND QUALITY ASSURANCE

11.1 Monitoring

Perrigo has ethical, legal and scientific obligations to carefully follow this study in a detailed and orderly manner in accordance with established research principles and FDA regulations. All medical records (source documents) of the subjects participating in this study must be presented for review and verification of eCRFs.

11.2 Auditing

Perrigo (or representative) may conduct audits at the study center(s). Audits will include, but are not be limited to, drug supply, presence of required documents, the informed consent process, and comparison of case report forms with source documents. The investigator agrees to participate with audits conducted at a reasonable time in a reasonable manner.

Regulatory authorities worldwide may also audit the investigator during or after the study. The investigator should contact Perrigo New York immediately if notified of such an audit, and must fully cooperate with the audits conducted at a reasonable time in a reasonable manner.

12. ETHICS AND RESPONSIBILITY

This study must be conducted in compliance with the protocol, the United States Food and Drug Administration (FDA) regulations, any other countries regulations, and ICH GCP Guidelines.

To compare the safety and efficacy profiles of Perrigo New York, Inc.'s Ingenol Mebutate Topical Gel 0.05% to Picato® Topical Gel 0.05% (Ingenol Mebutate Topical Gel 0.05%) and to demonstrate the superior efficacy of the two active formulations over that of the vehicle in the treatment of Actinic Keratosis.

3 Study Design

For the purpose of exploring the above objectives, the study will be conducted as a double-blind, randomized, parallel-group, vehicle-controlled, multicenter trial.

Each subject will be randomly assigned to one of following treatment groups :

- (1) Test: Ingenol Mebutate Topical Gel 0.05%, Perrigo New York, Inc.
- (2) Reference: Picato® Topical Gel 0.05% (Ingenol Mebutate Topical Gel 0.05%), Leo Pharma Inc.
- (3) Vehicle of test product, Perrigo New York, Inc.

Subjects will be admitted into the study only after written informed consent has been obtained and all of the inclusion and none of the exclusion criteria have been met. Randomization will be performed according to a computer generated randomization scheme where the treatment group designation has been assigned to the subject number. The treatment designation will remain blinded until the final database is closed. An independent third party will generate and hold the randomization code throughout the study. Randomized subjects will apply assigned

topical gel [redacted] once daily for two (2) consecutive days to the selected treatment area (one contiguous skin area of approximately 25cm² treatment area on the trunk/extremities) avoiding contact with the eyes, mouth and other body areas during and after gel application.

Subjects will be scheduled for an office visit for Visit 1/Day 1 (Baseline), Visit 2/Day 3 (±1 days) (Post-Treatment Interim), Visit 3/Day 29 (±3 days) (Interim), and Visit 4/Day 57 (±2 days) (End of Study). Safety will be assessed by monitoring adverse events at each visit and during a Follow-Up Phone Call/Day 15 (±3 days).

4 Populations To Be Analyzed

Three subject populations are defined as follows:

- (1) An intent-to-treat (ITT) subject is any individual who: (a) was randomized into the study, and (b) received and applied at least one dose of study medication;
- (2) A modified intent-to-treat (mITT) subject is any individual who: (a) was randomized into the study, (b) met eligibility criteria, (c) received and applied at least one dose of study medication, and (d) had at least one post-baseline efficacy assessment;
- (3) A per-protocol (PP) subject, consistent with the protocol, is one that: (a) met eligibility criteria, (b) was randomized into the study, received and used study medication, (c) applied the study medication on Days 1-2 [redacted] (d) completed Visit 4/Day 57 (End of Study/Early Termination Visit) within the ±2 days visit window OR was discontinued from the study due to treatment failure with a full compliance rate of 100%, and (e) did not have any significant protocol violations that could have interfered with the administration of the treatment or the precise evaluation of treatment efficacy.

5 Planned Analyses

5.1 Methodological Considerations

The study will be conducted under the same protocol across all the sites. No formal statistical analyses are planned to evaluate the consistency of efficacy results across the multiple clinical sites. These results, however, will be tabulated and if a site's efficacy data are obviously inconsistent with the results across all sites, this will be explored and addressed in the final study report.

Two-sided hypothesis testing will be conducted for all the tests. Resulting p-values less than 0.05 will be considered statistically significant unless noted otherwise. No adjustments of p-values for multiple comparisons will be made. No interim analyses are planned. SAS software will be used for all data analyses and tabulations.

5.2 Handling of Dropouts or Missing Data

For the efficacy variables, a last-observation-carried-forward (LOCF) approach for missing results will be used in the mITT analysis. For the PP subjects who discontinue due to treatment failure, the results observed from their last visit will be carried forward to all the subsequent missing visits.

For demographic and baseline characteristics and the safety profile, each variable will be analyzed using all available data. Subjects with missing data will be excluded only from the analyses for which data are not available.

5.3 Demographics and Baseline Characteristics

Baseline variables (e.g., sex, age, ethnic origin) will be evaluated, adjusting for site, to identify differences between treatment groups, which were not eliminated by randomization. Any significant baseline differences will be reviewed for their potential impact on the efficacy findings.

Continuous variables at baseline will be examined by two-way analysis of variance (ANOVA) with treatment and site as fixed effects when normal error and homogeneous variance assumptions are satisfied, or by the nonparametric rank based ANOVA when they are not, to compare treatment group differences.

Categorical variables such as gender, race, etc., will be examined by Cochran-Mantel-Haenszel test, stratified by site.

Summary tables by treatment group will be presented. For each continuous variable, the summary will include the mean, standard deviation, minimum and maximum. For each categorical variable, the summary will include frequencies and percentages.

5.4 Subject Accountability

A summary of subject disposition will be provided for all subjects. Descriptive summaries of subject disposition, reason for discontinuation, and analyses population will be provided by treatment group. The data will also be presented in subject data listings.

5.5 Efficacy Variables and Analyses

The primary efficacy measure is the proportion of subjects with clinical response of success defined as complete clearance (absence) of all clinically visible Actinic Keratosis lesions identified at the baseline visit and no new Actinic Keratosis lesions in the treatment area at Visit 4/Day 57.

Equivalent Efficacy

The compound hypothesis to be tested for clinical equivalence between test and reference is:

$$H_0 : p_T - p_R < -0.20 \text{ or } p_T - p_R > 0.20 \text{ versus}$$

$$H_A: -0.20 \leq p_T - p_R \leq 0.20.$$

Where p_T and p_R are the proportions of subjects with clinical success at Visit 4/Day 57 for the test and reference products, respectively. The test product will be considered to be clinically equivalent to the reference product if the 90% confidence interval (CI) on the difference in their rates of clinical success, calculated by Wald's method with Yates' continuity correction, is contained within the limits -0.20 to +0.20. Rejection of the null hypothesis supports the conclusion of therapeutic equivalence between the test and reference products for the primary efficacy variable.

[REDACTED]

Superiority

The hypotheses to be tested for superiority of the test and reference products over vehicle are:

$$H_0: p_T \leq p_V \text{ versus } H_A: p_T > p_V$$

$$H_0: p_R \leq p_V \text{ versus } H_A: p_R > p_V$$

Where p_T , p_R and p_V are the proportion of subjects with clinical success at Visit 4/Day 57 for the test, reference and vehicle products, respectively. The tests will be conducted independently for the test product and the reference product using two-sided, $\alpha = 0.05$, continuity-corrected Z-tests. Superiority will be established if the proportion of subjects with clinical success in the active treatment group is greater and statistically different than that in the vehicle. Rejection of the null hypothesis supports the conclusion of superiority of the test and reference products over the vehicle product for the primary efficacy variable.

[REDACTED]

5.6 Safety Variables and Analyses

Duration of Treatment and Medication Compliance

Number of applications, days of exposure, and compliance rate will be summarized by treatment group using descriptive statistics. For each subject, the overall duration of treatment (days) will be calculated using the following formula:

$$\text{(Date of last application of study medication)} - \text{(Date of first application of study medication)} + 1.$$

Medication compliance rate (%) will be calculated for each subject as follows:

$$\text{(Total number of applications used)} / \text{(Expected number of applications)} * 100\%.$$

Subjects who complete the study are expected to have 2 applications. [REDACTED]

[REDACTED] For prematurely discontinued subjects, expected number of applications will be determined based on the

overall duration of treatment by the time of discontinuation. Descriptive summaries of exposure and medication compliance rate will be provided by treatment group for the ITT subjects

Adverse Events

Adverse events (AEs) will be coded in MedDRA, version 15.1. Treatment-Emergent Adverse Event (TEAE) is defined as any AE occurs on or after applying the first dose of study drug. Number and percent of subjects reporting TEAEs will be tabulated by treatment group. Summaries will be presented by body system and preferred term for the ITT population, and further by severity and relationship to study medication. TEAEs reported by 5% or more subjects for any treatment group will also be summarized. In the summaries of incidence rates (frequencies and percentages), severity and relationship to study drug, subjects who report more than one event that are mapped to the same preferred term will be counted only once under the strongest severity and relationship, accordingly Fisher's exact test will be used to compare the proportions of subjects of the two active treatment groups who report any TEAE.

Treatment-Emergent Serious Adverse Events (TESAEs) will be discussed within the clinical study report. TESAEs and TEAEs that led to treatment interruption or discontinuation will be presented in data listings.

Concomitant Medications

Concomitant medications will be coded using the WHO Drug Dictionary, version September 2014, and will be presented in data listings.

Application Site Reactions

The severity of application site reactions such as erythema, flaking/scaling, crusting, swelling, vesiculation/pustulation, and erosion/ulceration will be summarized by treatment group and visit using frequencies and percentages of subjects.

Safety comparisons will be performed only for the ITT population.

6 Appendices

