5. PROCEDURES

5.1 Subject Screening and Enrollment

The study personnel will review the IRB approved informed consent form and assent form, if applicable, with each subject and give the subject an opportunity to have all questions answered before proceeding. The consent/assent form must be signed by each subject and witnessed before the subject is enrolled into the study. A copy of the signed consent/assent will be given to every subject and the original will be maintained with the subject's records. Subjects under the legal age of consent must sign an IRB approved written informed consent/assent in addition to a parent or legally authorized representative.

Subjects that require a wash-out [REDACTED] from their initial informed consent/assent signing must be re-consented before any further study procedures can begin.

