7.2 Definitions

An adverse event (AE) is defined as any untoward medical occurrence in a patient administered a medicinal product and which does not necessarily have to have a causal relationship with this treatment. An adverse event can therefore be any unfavorable and unintended sign (for example, an abnormal laboratory finding), symptom, or disease temporally associated with the use of a medicinal product, whether or not considered related to this medicinal product.

A serious adverse event (SAE) is an adverse event that results in any of the following outcomes:

- death
- life-threatening event (i.e., the subject was, in the opinion of the investigator, at immediate risk of death from the event as it occurred. It does not include an event that, had it occurred in a more severe form, might have caused death)
- requires in-subject hospitalization or prolongs hospitalization
- a persistent or significant disability/incapacity or substantial disruption of the ability to conduct normal life functions
- congenital anomaly/birth defect
- Other adverse events that may be considered serious when, based upon appropriate medical judgment, they may jeopardize the patient or subject or may require medical or surgical intervention to prevent one of the previously listed outcomes.

Immediately Reportable Adverse Events (IRAE): Any serious AE or any AE that necessitates discontinuation of study medication, including pregnancy.

Unexpected Adverse Event: An unexpected event is any adverse drug experience, the specificity or severity of which is not consistent with the current approved product labeling (package insert, Appendix D) for the study medication, the Investigator's Brochure, or as described in the clinical protocol and consent materials.

Intensity of Adverse Events: The maximum intensity of an AE during a day should be recorded on the eCRF. If the intensity of an AE changes over a number of days, then separate entries should be made having distinct onset dates for the changes in severity.

Mild - AEs are usually transient, requiring no special treatment, and do not interfere with subject's daily activities.

Moderate - AEs typically introduce a low level of inconvenience or concern to the subject and may interfere with daily activities, but are usually ameliorated by simple therapeutic measures.

Severe - AEs interrupt a subject's usual daily activity and traditionally require systemic drug therapy or other treatment.

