7.3 Eliciting and Reporting of Adverse Events

The investigator will periodically assess subjects for the occurrence of adverse events. In order to avoid bias in eliciting adverse events, the subject or parent/legally authorized representative should be asked a non-specific question (e.g., "How have you been feeling since your last visit?") to assess whether any AE has been experienced since the last visit. All adverse events (as defined in [Section 7.2](#)), either observed by the Investigator or one of his/her medical collaborators, or reported by the participant spontaneously, or in response to direct questioning, will be reported and documented in the source and the study reporting forms. When reporting an adverse event, the Investigator must assign a severity grade to each event and declare an opinion on the relatedness of the event to the study medication or procedure. Serious or unexpected adverse events must be reported to Perrigo and [REDACTED] **within 24 hours** of when the Investigator first learns of the occurrence of the event.

Adverse events will be documented in source and recorded in a timely manner on eCRFs. Adverse events (i.e., worsening of Actinic Keratosis*) that are identified at the last assessment visit (or the early termination visit), must be recorded on the AE eCRF with the status of the AE noted.

** Worsening of the subject's Actinic Keratosis may be expected from application of the study medication. Therefore, this will not be considered an AE unless one or more of the following occurs: 1) alternative treatment required; 2) subject is discontinued by the Principal Investigator for worsening of AK.*

Adverse event reporting begins from the signing of informed consent/assent. Adverse events should be followed until resolved or 30 days after the final study treatment. In any case, serious adverse events that are not resolved or considered to be chronic within 30 days of the final study treatment must be followed by the investigator until they become resolved or are considered to be chronic (stabilized for at least 30 days). All events that are ongoing at this time will be recorded as ongoing on the eCRF.

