6.1 Handling of Missing or Incomplete Dates for Adverse Events and Concomitant Medications

Adverse Events

Handling of partial dates is only considered for the start date. An adverse event with a partial start date is considered treatment emergent if:

- only the day is missing and the start month/year is the same or after the month/year of the first dose
- the day and month are missing and the start year is the same or greater than the year of the first dose date
- the start date is completely missing

Concomitant Medications

Handling of partial dates is only considered for the stop date. A medication with a partial stop date is considered concomitant if:

- only the day is missing and the stop month/year is the same or after the month/year of the first dose
- the day and month are missing and the stop year is the same or greater than the year of the first dose date
- the stop date is completely missing or the medication is ongoing

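### Applied entry by entry, the SAP's TEAE definition can flag an adverse event that began before dosing and only improved afterwards (minor)

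*SAP*

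**What the plan says.** Four rules bear on this point.

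- **Recording (Protocol 7.2, intensity of adverse events).** When the intensity of an event changes over several days, "then separate entries should be made having distinct onset dates for the changes in severity". Falls and rises are treated alike.
- **Start of collection (Protocol 7.3).** "Adverse event reporting begins from the signing of informed consent/assent". Events that begin before the first dose are therefore in the database.
- **Definition (SAP 5.6, Adverse Events).** "Treatment-Emergent Adverse Event (TEAE) is defined as any AE occurs on or after applying the first dose of study drug". There is no condition that the event be new or worse than before dosing.
- **Use (SAP 5.6).** "Fisher's exact test will be used to compare the proportions of subjects of the two active treatment groups who report any TEAE". The same flag feeds the tables by preferred term, severity and relationship, and the table of events reported by at least 5% of a group.

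SAP 6.1, on incomplete dates, shows which variable decides the flag. It lists conditions on the start date under which "An adverse event with a partial start date is considered treatment emergent if" is met. Neither document says how the several entries of one continuing event are to be joined.

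**The concern.** Each rule is ordinary alone. Together they leave a gap. A headache that was moderate before dosing and became mild a few days after it produces a second entry whose onset date falls after first dose. A program that compares each entry's start date with the first-dose date will flag that entry, although nothing emerged on treatment.

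The SAP's visible text tests one adverse event quantity between Test and Reference, the proportion of subjects with any TEAE. Entries that record only improvement add subjects to that proportion who do not belong there. Two programmers who read the definition differently could also report different counts from the same data.

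**Working it through.** The documents state no adverse event rate and the sample size section is redacted, so there is no figure to reproduce. The check is of the rules first, and then of the possible size under assumptions.

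**Step 1. Apply the rules to five histories.** Days are relative to first dose. The literal rule flags any entry that starts on or after first dose. The amended rule flags it only if the event is new or more intense than at its last pre-dose level.

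| History | Literal rule | Amended rule |
|---|---|---|
| Moderate from day -5, unchanged | not TEAE | not TEAE |
| Moderate from day -5, mild from day +3 | **TEAE** | **not TEAE** |
| Mild from day -5, moderate from day +3 | TEAE | TEAE |
| New, mild, on day +3 | TEAE | TEAE |
| Moderate from day -5, mild from day -2 | not TEAE | not TEAE |

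Only the second history differs.

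**Step 2. Does another rule catch it?** SAP 5.6 says that "subjects who report more than one event that are mapped to the same preferred term will be counted only once under the strongest severity and" (the sentence treats causal attribution in the same way). This collapses duplicates within a preferred term. It does not remove a subject whose only post-dose entry is an improvement, because that one entry already carries the flag.

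**Step 3. Who can be affected?** The event must start after consent, persist past first dose, and then drop to a lower grade. An event that resolves directly creates no further entry. SAP 3 lists no office visit before Visit 1/Day 1, and Protocol 5.11 has the first tube applied at that visit, so for many subjects the window may be only hours. It is longer for subjects with a wash-out: Protocol 9 requires consent before current medication is withdrawn, and Protocol 5.1 says that some wash-out subjects, counting "from their initial informed consent/assent signing must be re-consented before any further study procedures can begin". The length is redacted and the number of such subjects is not given.

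**Step 4. Illustrative size.** Let p be the true any-TEAE rate and q the share of subjects with an improvement-only entry, independent of p. Both are assumed.

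Observed rate = p + (1 - p)q

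| p | q = 1% | q = 3% | q = 5% |
|---|---|---|---|
| 10% | 10.9% | 12.7% | 14.5% |
| 30% | 30.7% | 32.1% | 33.5% |
| 50% | 50.5% | 51.5% | 52.5% |

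For example, 0.30 + 0.70 × 0.03 = 0.321.

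If q is the same in both arms, the observed difference is (1 - q) times the true difference. With assumed true rates of 30% and 45%, 15 points become 15 × 0.97 = 14.55 points at q = 3%. With those rates, an assumed 150 subjects per arm and a two-sided 0.05 level, exact enumeration gives this power for Fisher's test:

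| q | 0 | 1% | 3% | 5% |
|---|---|---|---|---|
| Power | 73.0% | 72.0% | 69.9% | 67.8% |

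**The case against.** The best counter-argument is that an entry is not an event. Protocol 7.2 speaks of one event whose intensity changes, and defines an adverse event as something untoward, which an improvement is not. Protocol 2.2 describes each event by one approximate onset date and one end date. On that reading the SAP's definition refers to the onset of the whole event, and the improving case is not treatment-emergent. This stands as a fair reading, and it is why the point is that misclassification can occur, not that it must. It does not close the gap: the SAP gives no rule for joining entries, and SAP 6.1 works from the start date.

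Other objections also stand in part.

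- The comparison in Protocol 2.2 and 8.1.5 is of any adverse event, which counts these subjects anyway. Only the SAP's TEAE version can change.
- No equivalence margin rests on the Fisher test, and safety is also judged on the nature, severity and frequency of events.
- The relationship table should help to separate events that began before dosing. It does not alter the any-TEAE count.
- The six listed application site reactions are generally not recorded as adverse events (Protocol 5.10) and are summarized separately.

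A reader might infer that every subject with such an entry is miscounted. The formula says otherwise: a subject who also has a genuine TEAE is already correctly in the any-TEAE proportion, so only the share (1 - p) of affected subjects is added. A reader might also infer that the 5% table is distorted. That table works by preferred term, so an assumed q of 1% to 3% could at most tip a term already near the threshold.

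**Conclusion.** The concern holds as a gap in the definition, at minor priority. Applied literally to the entries that Protocol 7.2 requires, SAP 5.6 can label an improving pre-dose event as treatment-emergent, and no other visible rule prevents it.

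The effect is probably small and mainly confined to wash-out subjects. Every figure above rests on assumed p, q and number per arm; none comes from the documents.

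A reader might go further and infer a biased safety comparison or a spurious Test-Reference difference. The documents do not support that. Nothing suggests that pre-dose events would be more common in one randomized arm, and if q is equal across arms the effect is a slight dilution of any true difference. The efficacy analyses do not use the flag.

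**What to change.** In SAP 5.6, define a TEAE as an adverse event that first starts, or increases in intensity over its last pre-dose level, on or after the first dose. Add that an entry made only because intensity fell is not treatment-emergent.

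Identify such entries from the records already collected: same subject, same preferred term and adjoining dates, with the matches reviewed before unblinding. Protocol 8 has the SAP finalized before database lock and unblinding, so the change fits there. No change to the protocol or the eCRF is needed; a parent-event field would be out of proportion to the effect.

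The cost is a little extra programming and a short blinded review. Matching on term and dates carries a small risk of joining two distinct events, which the review should limit.
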